#### 11.2.4 Participants with moderate or severe OSA as per AASM 2012

Participants with mild OSA (AHI 5-15) or no OSA (AHI 0-4) as per AASM 2007 who have moderate or severe OSA (AHI >15) when re-scored as per AASM 2012 will be analysed as per the secondary outcomes. As this group is likely to be quite small, all analysis will be exploratory only.

## 12 Statistical Analysis Plan

A separate Statistical Analysis plan will be developed and published prior to the end of the trial.

## 13 Risks and Benefits

### 13.1 Anticipated Clinical Benefits

Participants may experience an improvement in quality of life based on treatment of their OSA.

### 13.2 Anticipated Adverse Device Effects

CPAP is known to be safe and is routine standard of care for the treatment of sleep disordered breathing

- Known side effects which can result from masks are:
  - Skin marks and irritation around the nose from the mask
  - Eye irritation, caused by leakage of air from the mask
- With careful fitting of the mask the risks are minimised

The common CPAP side effects are:

- Drying of the nose, mouth, or throat
- Nosebleed
- Bloating
- Ear or sinus discomfort
- With correct therapy settings and the use of humidification the risks are minimised

### 13.3 Residual Investigational Device Risks

- The devices used in this study are commercially available CE marked CPAP devices for the treatment of OSA in adults. There are no residual investigational device risks.

### 13.4 Risks associated with Study Participation

- There are no identified risks associated with study participation. Participants randomised to the control group will wait the three month study duration before they have access to CPAP treatment. However this is deemed acceptable as CPAP treatment is not standard routine care for these patients, and, depending on the clinic, some may never be offered CPAP treatment.

- Potential participants who may pose a risk to others through excessive sleepiness or concerns about sleepy driving will be excluded from the study
- Ethics committee approval will be obtained before patient enrolment to the study

### 13.5 Data Safety Monitoring Committee (DSMC)

- Due to the low risk nature of this trial, the fact that all products are commercially available and are being used as per their intended use, combined with the short duration of subject participation, there is no requirement for a DSMC.

### 13.7 Safety Reporting

Definitions of Serious Adverse Events:

Any untoward medical occurrence that:

- results in death
- is life-threatening
- requires in-patient hospitalization or prolongation of existing hospitalization (voluntary hospitalisations for elective surgeries are not considered as serious adverse events)
- results in persistent (symptomatic or moderate) or significant disability /incapacity
- an important medical event; or
- is a congenital anomaly/birth defect

Important medical adverse events are those which may not be immediately life-threatening, but are clearly of major clinical significance. They might jeopardise patients' safety and might require intervention to prevent any serious outcomes listed above.

#### Reporting Serious Adverse Events

- 1) All known details of the SAE should be notified to the clinical trials unit as soon as becoming aware. The CTU will pass this information to the sponsor within 24 hours of being notified
- 2) The sponsor (ResMed) is responsible for sending all information to ResMed's Regulatory department within 10 days to ensure correct regulatory reporting  
The SAE is followed to completion  
A serious adverse event (SAE) occurring to a participant should be reported to the REC that gave a favourable opinion of the study where in the opinion of the Chief Investigator the event was 'related' (resulted from administration of any of the research procedures) and 'unexpected' in relation to those procedures. Reports of related and unexpected SAEs should be submitted

within 15 working days of the Chief Investigator becoming aware of the event, using the HRA report of serious adverse event form (see HRA website).

## 15. Protocol Versions

Version	Change
1.0	Original Version
2.0	
Section 10 (Questionnaires)
 
 
• Addition of the EQ-5D questionnaire
 

3.0	
Front page Change of trial statistician
 
Section 5 (Study Methods) Clarification that AHI given by automatic scoring will be used for the primary and secondary outcomes, and that AHI given by review of the central scorer will be reported as a secondary outcome Update to text and trial figures to clarify this information
 
Front of page 1 and Section 13.6 (Trial Steering Committee) Updated list of TSC members
 
Section 5.7 (3 month visit) Participant weight to be collected at 3 month visit.
 
Section 6 Clarification of central scorer
 
Section 11 Updated sample size section with new estimation of required number of participants

4.0	Weight added to section 5.7, this was omitted in error in the previous amendment
5.0	
Section 5.3 (Home Sleep Test Scoring Review) and Section 6.1 (Study Responsibilities: Terms and Tasks) Clarification of the role of the expert Central Scorer and the review of the automated AASM 2012 scoring
 
Page 1 and Section 13.6 (Trial Steering Committee) Updated list of TSC members

1. INTRODUCTION

This document details the proposed presentation and analysis for the main paper(s) reporting results from the ResMed funded multi-centre, unblinded, randomised, controlled trial of the effect of positive airway pressure on energy and vitality in mild Obstructive Sleep Apnoea (OSA) patients (The MERGE study). The results reported in these papers should follow the strategy set out here. Subsequent analyses of a more exploratory nature will not be bound by this strategy, though they are expected to follow the broad principles laid down here. The principles are not intended to curtail exploratory analysis (for example, to decide cut-points for categorisation of continuous variables), nor to prohibit accepted practices (for example, data transformation prior to analysis), but they are intended to establish the rules that will be followed, as closely as possible, when analysing and reporting the trial.

The analysis strategy will be available on request when the principal papers are submitted for publication in a journal. Suggestions for subsequent analyses by journal editors or referees, will be considered carefully, and carried out as far as possible in line with the principles of this statistical analysis plan.

Any deviations from the statistical analysis plan will be described and justified in the final report of the trial. The analysis should be carried out by an identified, appropriately qualified and experienced statistician, who should ensure the integrity of the data during their processing. Examples of such procedures include quality control and evaluation procedures.

2. CHANGES FROM PREVIOUS VERSION OF SAP

The Statistical Analysis Plan (SAP) has been re-evaluated and modified since Version 1.2, because of a change in statistical representation for study oversight.

3. GLOSSARY OF ABBREVIATIONS

ABBREVIATION	DESCRIPTION
AASM	American Association of Sleep Medicine
BMI	Body Mass Index
CC	Completed Cases

ABBREVIATION	DESCRIPTION
CPAP	Continuous Positive Airway Pressure
Euroqol EQ-5D	5 Dimension Health Questionnaire
ESS	Epworth Sleepiness Scale
FOSQ	Functional Outcomes of Sleep Questionnaire
FSS	Fatigue Severity Scale
HADS	Hospital Anxiety and Depression Scale
HST	Home Sleep Test
ISI	Insomnia Severity Index
ITT	Intention to Treat
MAR	Missing at random
MCS	Mental Component Summary
ORTU	Oxford Respiratory Trials Unit
OSA	Obstructive Sleep Apnoea
PCS	Physical Component Summary
PP	Per Protocol
PROM	Patient Reported Outcome Measure
SAP	Statistical Analysis Plan
SF-36	Short Form (SF) – 36 Questionnaire
TSC	Trial Steering Committee
VAS	Visual Analog Scale

4. STUDY DESIGN

4.1 Background

Patients with Obstructive Sleep Apnoea (OSA) experience interrupted and reduced sleep which can have a significant impact on quality of life and increases the risk of developing certain conditions. Mild OSA, unlike moderate and severe OSA, has not been extensively studied. Although there is a reasonable pool of evidence that suggests that even minor sleep related breathing disturbances are associated with negative consequences, there is no consensus on when treatment should be initiated or the best treatment for mild OSA patients. Two previous clinical trials have suggested that treating mild OSA with Continuous Positive Airway Pressure (CPAP) improved symptoms, quality of life and reduced health risks in these patients. However, despite this evidence, treatment with CPAP for mild OSA is not consistently offered.

CPAP is a treatment that uses mild air pressure to keep the airways open during sleep. The machine (ResMed AirSense S10) consists of a mask that fits over the nose, a tube that connects the mask to the machine motor and the motor which blows air through the tube to the mask.

Mild OSA is defined as Apnoea Hypopnoea Index (AHI) of 5 up to 15 events/hour. Mild OSA patients will be identified using **American Academy of Sleep Medicine (AASM)** 2007 and 2012 guidelines as described below.

In 2012, the American Academy of Sleep Medicine (AASM) changed the criteria needed to score a hypopnoea during a sleep study. Previous 2007 criteria had required a hypopnoea to include a decrease in oronasal airflow by $\geq 30\%$ from baseline, an event of at least 10 seconds, and $\geq 4\%$ SpO₂ desaturation. These criteria had been widely accepted by healthcare providers to form the basis of

diagnosis, access to treatment, and reimbursement for patient equipment. In 2012, a change was made to these criteria which permitted hypopnoeas to be scored with an arousal only, or an oxygen desaturation of $\geq 3\%$. The newer criteria of OSA defined by the AASM in 2012 are broader and increase the percentage of patients who may be diagnosed with OSA, potentially by up to 40%.

Guideline	Recommended Hypopnea Definition per Guidelines:
AASM 2007	
 • A decrease in oronasal airflow by $\geq 30\%$ from baseline AND • The event is ≥ 10 sec long AND • Associated with $\geq 4\%$ SpO_2 desaturation
AASM 2012	
 • A decrease in oronasal airflow by $\geq 30\%$ from baseline AND • The event is ≥ 10 sec long AND • Associated with $\geq 3\%$ SpO_2 desaturation OR arousal

However, the new scoring rules remain controversial as there is no compelling evidence that patients with mild OSA according to this new criterion benefit from treatment. As a result, health insurance reimbursement rules in some countries have not adopted the 2012 criteria.

In the MERGE Trial, the patients are initially screened for eligibility based on automatic AASM 2007 scoring. Those who meet the criteria for Mild OSA (AHI 5-15 events/hr) based on AASM 2007 scoring using the ApnoeaLink home sleep test (automatically scored by Airview software) are eligible for enrolment. Those patients who have no OSA (AHI < 5 events/hr) per AASM 2007 scoring are rescored using AASM 2012 automated scoring. Those patients who meet the criteria of AHI ≥ 5 events/hr per AASM 2012 are also eligible for enrolment.

4.2 Enrolment Target and Inclusion/Exclusion Criteria

The MERGE study is a prospective multicentre randomised parallel trial with 3 months of active treatment versus a control arm. Randomisation with minimisation will be performed with a 1:1 treatment group allocation.

Date of start of recruitment:	26 October 2016
Date of expected end of recruitment:	31 December 2018
Date expected end follow-up:	31 March 2019
Target number of subjects:	224 (112 per arm)
Participating Centres:	11

A patient will be eligible for inclusion in the study if all the following inclusion criteria apply:

- AHI 5-15 events/hr as per AASM 2007 scoring criteria or AHI ≥ 5 per AASM 2012 if AHI 0-4.9 per AASM 2007
- Aged ≥ 18 and ≤ 80 years
- Ability and willingness to provide written informed consent
- Ability to tolerate a CPAP one hour long run-in test

A patient will not be eligible for the study if any of the following exclusion criteria apply:

- The presence of unstable cardiac disease at trial screening
- Inability to give fully informed consent
- Use of supplemental oxygen
- Secondary sleep pathology e.g. Periodic Limb Movement Syndrome, Narcolepsy, Circadian Disorder, Obesity Hypoventilation Syndrome
- Epworth Sleepiness Scale (ESS) ≥ 15 , or concerns about sleepy driving from physician/ sleep lab staff
- Body Mass Index (BMI) $\geq 40 \text{ kg/m}^2$
- Previous CPAP usage

4.3 Treatment Groups

The Treatment group will receive CPAP along with standard care for mild OSA patients (counselling on healthy lifestyle behaviours and sleep hygiene habits). The Control group will receive only standard of care for OSA patients.

4.4 Description of Adherence in Treatment Group

Adherence with CPAP in the Treatment group will be defined as follows. Patients in the Treatment group will be considered adherent to CPAP if the patient uses the device at least 4 hours per day on average during the 3-month study period.

The US Medicare definition for adherence will be considered as a secondary definition for exploratory analyses. By this definition, patients who use the device at least 4 hours per night for 70% of the nights during a 30-day period over the 3-month study period are considered adherent.

Adherence to CPAP will be monitored using ResMed AirView Remote Monitoring system. Daily usage data over the study period will be provided for analysis.

4.5 Study Objectives

This study aims to assess the changes in quality of life from baseline to 3 months in mild OSA patients (based on AASM 2012 guidelines) comparing the Treatment and Control groups.

The objectives of the study are as follows:

Primary Objective:

- Compare the change in quality of life (SF-36 energy and vitality subscale score) from baseline (pre-treatment) to 3 months between Treatment and Control groups in patients with mild OSA **per AASM 2012** guidelines.

Secondary Objectives:

- Compare changes in quality of life scores (SF-36, ESS, FSS, FOSQ, HADS, ISI and EQ-5D) from baseline (pre-treatment) to 3 months between Treatment and Control groups in patients with mild OSA **per AASM 2012** guidelines.
- Compare changes in quality of life scores (SF-36, ESS, FSS, FOSQ, HADS, ISI and EQ-5D) from

baseline (pre-treatment) to 3 months between Treatment and Control groups in patients with mild OSA **per AASM 2007 guidelines**.

Exploratory Analyses:

- Compare changes in quality of life scores (SF-36, ESS, FSS, FOSQ, HADS, ISI and EQ-5D) from baseline (pre-treatment) to 3 months between Treatment and Control groups in patients with moderate to severe OSA **per AASM 2012 guidelines**.
- Compare changes in quality of life scores from baseline to 3 months between Treatment and Control groups for patients with no OSA ($AHI < 5$) **per AASM 2007 guidelines** but who enter the study ($AHI \geq 5$) **per AASM 2012 guidelines**.
- Assess the impact of adherence to CPAP in the Treatment group, comparing changes in quality of life scores from baseline to 3 months for patients adherent and not adherent to CPAP over the course of study.
- Explore variation in the treatment effect on the change in quality of life scores (SF-36 energy and vitality subscale score, ESS, and FSS) from Baseline to 3 months over the continuous baseline measures of age, BMI, and AHI (as a continuous measure of OSA severity), separately for AASM 2007 and AASM 2012 guidelines.
- Assess the number of patient telephone contacts, clinic visits and other types of intervention required to support CPAP adherence, including the impact of missed contacts, in the Treatment group, comparing results between patients adherent and not adherent to CPAP.
- Compare baseline symptoms and changes in quality of life scores from baseline to 3 months between Treatment and Control groups by gender.
- Compare change from baseline to 3 months in weight and BMI between Treatment and Control groups.
- A cost effectiveness and health economic analysis will be performed by an outside consultant. Details of this analysis will be provided in a separate analysis plan.

4.6 Sample Size

The sample size of 224 (112 per arm) is based on statistics observed in the MOSAIC study: a mean score difference of 6.6 was observed between 3 months and baseline (considered a significant clinical improvement by the authors of the study) in the Energy and Vitality subscale of the SF-36 questionnaire, with a mean change of 4.2 (SD 18.1) in the Control group and 10.8 (SD 17.0) in the CPAP Treatment group. The sample size calculation is based on a two-sided 5% significance level and 80% power.

It is estimated that approximately 300 participants will need to be randomised in order to reach the required sample size of 224 patients with mild OSA **per AASM 2012 guidelines**. Subjects who are eligible for Home Sleep Testing (HST) are evaluated for their level of OSA. Those patients who have Mild OSA **per AASM 2007 guidelines** are eligible for randomisation. Those patients who have No OSA **per AASM 2007 guidelines** are further assessed based on the AASM 2012 guidelines. All patients with

AHI \geq 5 per AASM 2012 guidelines are also eligible for randomisation. Since the primary endpoint analysis is based on patients with mild OSA per AASM 2012 guidelines, there will be some patients randomised who will not fall into this sample, thus the need for additional enrolment. Additionally, it is expected that 10% of those randomised will drop-out before the end of the study.

The number of patients required to enrol will be reviewed and updated by the Trial Steering Committee (TSC) as new recruitment information accumulates. This will not change the goal of 224 patients completing the study who had mild OSA per the AASM 2012 guidelines.

4.7 Randomisation

Randomisation was carried out using the RRAMP randomisation system provided by the Oxford Respiratory Trials Unit (ORTU). Minimisation method was used to allocate patients to treatment and control groups, maintaining balance in the following three stratifying factors:

- Gender: male; female.
- Age: <30 years, 30-60 years, >60 years
- BMI: <30 kg/m², \geq 30 kg/m²

4.8 Definitions of Study Endpoints

Patient outcome measures are generated from six quality of life questionnaires. All outcome measures are Patient Reported Outcome Measures (PROMs). Each questionnaire, when fully completed provides one or more summary scores as detailed below.

1. **Short Form 36 (SF-36):** The Short Form (SF-36) Health Survey is a 36-item, patient-reported survey of patient health consisting of eight subscales and two summary scores. The survey determines the general quality of life of a patient based on 8 subscales (Bodily Pain, Energy/Vitality, General Health, Mental Health, Physical Functioning, Role Emotional, Role Physical and Social Functioning), and a physical component summary (PCS) score and mental component summary (MCS) score. Secondary analysis will use both the 8 subscales and the MCS and PCS summary scores. These scores will be calculated using PRO CoRE Smart Measurement® System software developed by OPTUM® and presented as norm-based scores.
2. **Epworth Sleepiness Scale (ESS):** The ESS form is a measure of a patient's likelihood to fall asleep in eight different scenarios. It is used in sleep clinics to detect dangerous levels of sleepiness in patients with sleep disorders and the summary score is an integer value of the total score of all questions ranging from 0 to 24.
3. **Fatigue Severity Scale (FSS):** The FSS is designed to measure the severity of fatigue and how it impacts an individual's daily life in terms of motivation, exercise, daily activity, work, family and social life. It consists of 9 questions with a total score ranging from 9 to 63, with higher scores associated with more fatigue. Secondary analysis will be performed on the total FSS score.
4. **Functional Outcomes of Sleep Questionnaire (FOSQ):** The FOSQ is a questionnaire designed to assess the impact of excessive sleepiness on multiple activities of everyday living. The FOSQ contains 30 items summarized as one total score and five subscales (Activity Level, Vigilance, Intimacy Relationships and Sexual Activity, General Productivity, and Social Outcome). Secondary analysis will be performed on the total FOSQ score.
5. **Hospital Anxiety and Depression Scale (HADS):** The HADS questionnaire contains 14 items in

which patients must respond on a scale of 0 to 4 to describe their current state of being. Two scores are calculated, one for depression and one for anxiety, both ranging from 0 to 21 with larger scores representing higher levels of anxiety/depression. Secondary analysis will be performed separately on the Anxiety and Depression scores.

6. **Insomnia Severity Index (ISI):** The ISI seven-item questionnaire asks the individual to rate the level of insomnia and perceptions of sleep problems in the last two weeks on a scale of 0 to 4. The total score ranges from 0 to 28 with larger scores indicating more severe insomnia. Secondary analysis will be performed on the total ISI score.
7. **European Quality of Life 5 Dimensions Questionnaire (Euroqol EQ-5D):** The Euroqol EQ-5D questionnaire consists of five dimensions assessing mobility, self-care, usual activities, pain/discomfort and anxiety/depression. Each dimension has 5 response levels ranging from no problems to extreme problems. The five dimensions are compiled to generate an EQ-5D Index. The second part of the questionnaire uses a Visual Analog Scale (VAS) to assess the patient's current health status on a scale of 0 to 100. Secondary analysis will be performed on the EQ-5D Index and VAS score.

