## 11.2 Sample Size calculation

### 11.2.1 Primary Endpoint Calculation

The primary outcome for this evaluation is the Energy and Vitality subscale of the SF-36 questionnaire. Previous clinical trials considering CPAP outcomes in mild OSA patients were reviewed. The MOSAIC study, which has the most similar patient selection criteria, reported an increase in vitality score of 10.8 (SE 1.3) points between baseline and 6 months in the CPAP group, compared with an increase of 4.2 (SE 1.4) in the standard care group. This difference between the treatment groups of 6.6 is considered a significant clinical improvement.

The sample size was calculated using a difference in treatment effect of 6.6 comparing CPAP change between 3 months and baseline (mean change 10.8, SD 17.00) to standard care change between 3 months and baseline (mean change 4.2, SD 18.1) with a 5% significance level and 80% power.

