### 11.2.2. Clinical significance of the primary endpoint

A mean change of 6.6 was considered clinically significant by the MOSAIC authors; however a universally agreed clinically significant score change does not currently exist. Minimal Clinically Important Difference (MCID) is a way of calculating the sample size based on the smallest change in a treatment outcome that a patient would identify as important. While a MCID has not been established for treatment of OSA, an expert panel has attempted to define consensus on a change in SF-36 which would be meaningful to a patient with chronic lung disease or asthma. The smallest MCID accepted by the panel was 10 for both COPD and asthma. While it is unclear if these scores can be extrapolated to OSA, this gives a reasonable indication that a score change of 6.6 points in this clinical trial considered to have a positive benefit on patients' lives

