4.9 Primary Hypothesis and Study Endpoints

Primary Study Hypothesis

The CPAP Treatment group will have greater improvement on the SF-36 Energy and Vitality subscale score in patients with mild OSA **per AASM 2012 guidelines** compared to the Control group.

Primary Endpoint

Change in the Energy and Vitality Subscale Score of the SF 36 questionnaire from baseline (pre-treatment) to 3 months in mild OSA patients **per AASM 2012 guidelines**.

Secondary Endpoints

Change in outcome scores between baseline (pre-treatment) and 3 months in mild OSA patients **per AASM 2012 guidelines** in using the following quality of life measures:

SF-36 (7 subscales not previously assessed as the primary endpoint, PCS and MCS summary scores)
ESS
FSS total score
FOSQ total score
HADS Anxiety and Depression scores
ISI total score
Euroqol EQ-5D index
VAS score

Change in outcome scores between baseline (pre-treatment) and 3 months in mild OSA patients **per AASM 2007 guidelines** in the following quality of life measures:

SF-36 (8 subscales, PCS and MCS summary scores)
ESS

FSS total score
 FOSQ total score
 HADS Anxiety and Depression scores
 ISI total score
 Euroqol EQ-5D index
 VAS score

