5.7 Primary Endpoint Analysis

The primary endpoint measure is the change in the Energy and Vitality subscale of the SF-36 questionnaire from baseline (i.e., pre-treatment) to 3 months post-randomization. It is a continuous variable.

The primary endpoint will be analysed using a mixed-effects repeated measures model to account for missing values. The model will be set up as follows: The Energy and Vitality subscale is the dependent variable, visit (baseline and month 3) is the repeated measure (a fixed effect), subject and site are random effects (with subject nested in site) and treatment group by visit is a fixed effect. In the case that the primary endpoint was not homogeneous across study sites (as discussed in Section 5.3), a treatment by visit by site interaction will also be included in the primary endpoint model as a random effect. Results will be presented as the mean difference in the change score from baseline to 3 months (adjusted for baseline score, as appropriate) between the two treatment groups with a 95% confidence interval at 3 months and p-value for the treatment group effect.

As a sensitivity analysis of the primary endpoint, a similar mixed-effects repeated measures model to the above will be constructed, that also adjusts for other baseline and demographic variables that were found to be imbalanced between treatment groups per Section 5.6. The mean difference in change score from baseline to 3 months will be presented with a 95% confidence interval at 3 months.

For these analyses of the primary endpoint, a P-value of less than 0.05 will be used to indicate statistical significance. Analyses of the primary endpoint will be generated for the ITT-1 population.

A second sensitivity analysis for the primary endpoint will be generated using the CC-1 population.

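### Does it matter that the SAP reports SF-36 scores as norm-based while the metric of the 6.6-point planning difference is never named?

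*SAP*

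**What the plan says.** SAP 4.8, the section that defines the endpoints, lists eight SF-36 subscales, Energy/Vitality among them. It continues "Secondary analysis will use both the 8 subscales and the MCS and PCS summary scores", and the next sentence says these scores come from named software "and presented as norm-based scores". Neither document mentions any other SF-36 metric.

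SAP 4.9 uses Energy/Vitality twice: as the primary endpoint in mild OSA by AASM 2012, and as one of the eight subscales in the secondary analysis of mild OSA by AASM 2007. SAP 5.7 makes the subscale the dependent variable of the primary model without repeating the metric. On reporting it says: "Results will be presented as the mean difference in the change score from baseline to 3 months", with a 95% confidence interval and a p-value. Significance is declared at p < 0.05.

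The planning figures are in SAP 4.6: a difference of 6.6, "with a mean change of 4.2 (SD 18.1) in the Control group and 10.8 (SD 17.0) in the CPAP Treatment group". Protocol 11.2.1 gives the same figures and adds: "This difference between the treatment groups of 6.6 is considered a significant clinical improvement". Protocol 11.2.2 sets 6.6 beside an expert-panel threshold of 10 from other diseases and speaks of "a score change of 6.6 points in this clinical trial considered to have a positive benefit". The Protocol calls these points. Neither document says whether they are raw or norm-based points.

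**The concern.** Two things look unsettled.

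- **Primary score.** The sentence just before the norm-based statement is about secondary analysis, and SAP 5.7 is silent. On a strict reading the primary score has no stated metric, and one subscale could be reported in different units for the two AASM populations.
- **Planning figures.** If the primary result is norm-based and 6.6 is a raw-scale figure, the two cannot be set side by side. A trial that reproduces its planned effect exactly could print a smaller number, with a confidence interval that might lie wholly below 6.6. Since Protocol 11.2.2 discusses 6.6 under the heading of clinical significance, some readers would make that comparison and could conclude that a planned-size benefit had fallen short.

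If the sample size also mixed two metrics, the 224 itself would be in doubt.

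**Working it through.** **Inputs.** Mean changes 10.8 and 4.2, SDs 17.0 and 18.1, two-sided 5%, 80% power (SAP 4.6); SEs 1.3 and 1.4 (Protocol 11.2.1); 1:1 allocation (SAP 4.2).

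**1. Reproduce the sample size.**
- Pooled SD of change = sqrt((17.0² + 18.1²)/2) = 17.56.
- n per arm = 2 × [17.56 × (1.960 + 0.842)/6.6]² = 111.1, so 112 per arm and 224 in total, as stated. Power at 112 is 80.3%. (The t-based calculation gives 79.97% at 112, and 113 per arm.)

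**2. Are the difference and the SDs on one metric?** Yes, as far as the documents show.
- 10.8 − 4.2 = 6.6.
- The SDs agree with the SEs quoted for those same changes: (17.0/1.3)² = 171 and (18.1/1.4)² = 167 patients. These total 338, a plausible number of analysed patients in an earlier trial of 391 (Protocol 3.1).
- So the calculation mixes no units.

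**3. Effect of the metric on design and test.** Take the norm-based subscale score to be a linear rescaling of the raw one, with slope k. The difference, its SD and its SE are all multiplied by k.
- 6.6k/17.56k = 0.376 for every k, so n stays at 112 per arm.
- The test statistic is unchanged, and so are the p-value and the power.

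**4. Which metric do the planning SDs suggest?** Assume a norm-based SD of 10 at each visit (not in the documents). The SD of change would be 10 × sqrt(2(1 − r)): 14.1 at r = 0, 10.0 at r = 0.5 and 7.7 at r = 0.7. The planning SDs exceed all three. In the other direction, 17.0 and 18.1 imply single-visit SDs of 12.0 and 12.8 at r = 0, and of 17.0 and 18.1 at r = 0.5. A raw scale fits better, but this is an inference. A patient group need not have the reference SD, and at r = 0 the implied values are not far from 10.

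**5. What a cross-metric comparison would look like.** SE = sqrt((17.0² + 18.1²)/112) = 2.346. The half-width is 1.971 × 2.346 = 4.62. An observed raw difference of exactly 6.6 has a 95% interval of 1.98 to 11.22. The documents do not give k, so a range is assumed:

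| k (assumed) | Printed difference | Printed 95% interval |
|---|---|---|
| 1 (raw) | 6.60 | 1.98 to 11.22 |
| 0.67 (10/15) | 4.40 | 1.32 to 7.48 |
| 0.50 (10/20) | 3.30 | 0.99 to 5.61 |
| 0.40 (10/25) | 2.64 | 0.79 to 4.49 |

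The interval falls wholly below 6.6 when k < 6.6/11.22 = 0.588. In every row it excludes zero by the same number of standard errors.

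**6. Does the plan use that comparison?** No. SAP 5.7 sets one criterion, p < 0.05, and does not mention 6.6. Protocol 11.2.2 says that no universally agreed threshold exists and that it is unclear whether the panel's values carry over to OSA. There 6.6 justifies the planning difference. It is not a threshold for success.

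**The case for a change.** The best case for a change is that it costs a few words and that the misreading is real. Only SAP 4.8 names a metric, the figures of 6.6 and 10 have none, and step 5 shows that for k below 0.588 a planned-size result would appear to miss 6.6 entirely. The standardised effect size added in the SAP 8 amendment gives a unit-free comparison, but nothing ties it to the planning value or warns against comparing points across metrics.

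Part of this stands. The metric of 6.6, its SDs and the threshold of 10 is named nowhere, and SAP 5.7 does not repeat the metric of SAP 4.8.

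The rest is weaker. That the primary score has no metric is overstated: SAP 4.8 is the endpoint-definition section, its list includes Energy/Vitality, and norm-based is the only metric on offer. Its remarks about secondary analysis recur for most of the other questionnaires and do not set the primary score apart. Reporting one subscale in two units would need a second scoring method that neither document mentions. Listing the subscale as primary in one population and secondary in the other reflects two populations.

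The unit-free route also needs care. The value 0.376 matches the amendment's mixed-model effect size only if the model's SE reflects the unadjusted SD of change. SAP 5.7 allows baseline adjustment. With it, the matching value would be 0.376 × sqrt(2/(1 + r)), that is 0.466, 0.434 and 0.408 at assumed r of 0.3, 0.5 and 0.7.

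**Conclusion.** No change to the plan is needed. The omission is one of labelling, and analysts can fill it sensibly: score every SF-36 subscale as SAP 4.8 says, in both AASM populations, and check the metric before setting any result beside 6.6.

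The size of the effect on the trial's conclusion is nil. The 224, the 80% power, the test and the p-value are the same on either metric, given that the norm-based score is a linear rescaling of the raw one. No rule in either document compares the estimate with 6.6. The possible misreading in step 5 rests on a norm-based SD of 10 and on k between 0.67 and 0.40, neither of which is in the documents, and on a reader ignoring the norm-based label that SAP 4.8 calls for. Following the plan as written gives a sound estimate and a sound conclusion.
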